## **2.2 Secondary Objective**

- To evaluate the continued response to long-term pimavanserin treatment in children and adolescents with ASD

### **2.2.1 Secondary Endpoint**

- Proportion of subjects who have at least 25% reduction from the antecedent study Baseline in the Aberrant Behavior Checklist–Irritability (ABC-I) subscale score AND a Clinical Global Impression–Improvement (CGI-I) of irritability score of 1 (very much improved) or 2 (much improved) compared to the antecedent study baseline status at Week 52.

## **2.3 Exploratory Objectives**

- To evaluate the continued benefit of long-term pimavanserin treatment on the symptoms of ASD, in children and adolescents with ASD in the following clinical areas:
  - Aberrant Behavior Checklist (ABC) symptom domains
  - Maintenance of benefit
  - Response to treatment

### **2.3.1 Exploratory Endpoints**

- Change from Baseline at Week 52 in the caregiver-rated ABC subscale scores:
  - Irritability
  - Stereotypic behavior
  - Lethargy
  - Hyperactivity
  - Inappropriate speech
- Change from Baseline at Week 52 in the Clinical Global Impression–Severity (CGI-S) of irritability score
- CGI-I of irritability score from the antecedent study Baseline at Week 52
- Change from Baseline at Week 52 in the Caregiver Strain Questionnaire (CGSQ)
- Proportion of subjects who have at least 25% reduction from the antecedent study Baseline in the ABC-I subscale score (ABC-I responders) at Week 52

- Proportion of subjects who have CGI-I of irritability score of 1 (very much improved) or 2 (much improved) compared to the antecedent study baseline status (CGI-I of irritability responders) at Week 52

### 3 STUDY DESCRIPTION

#### 3.1 Overview of Study Design

This study will be conducted as a 52-week, open-label extension study of the antecedent double-blind study to determine the long-term safety and tolerability of pimavanserin for the treatment of irritability associated with ASD in children and adolescents (5 through 17 years old at the time of enrolling into the antecedent double-blind study). Approximately 60 global sites and approximately eight countries will participate in this study.

The duration of participation for individual study subjects will be up to approximately 56 weeks. The total duration of exposure to pimavanserin may be greater than 52 weeks (e.g., up to 58 weeks) as some subjects have been treated with pimavanserin in an antecedent double-blind study.

The study will have two periods:

- Open-label treatment period (52 weeks)
- Safety follow-up period (at least 30 days)

Subjects who have completed the antecedent double-blind study and who have shown no significant worsening of symptoms at the end of the study as evidenced by the CGI-I of irritability will be included in this long-term extension study.

Study ACP-103-070 subjects must be consented prior to the procedures being performed at the End of Treatment (EOT) visit in the antecedent double-blind study. Procedures performed at the EOT visit of the antecedent double-blind study will be carried over to the ACP-103-070 study to be included as baseline information, and this visit will be considered the Baseline Visit (Visit 1) of the ACP-103-070 study.

The study start date is defined as the date the first subject is enrolled, which is the baseline visit date for the first subject for this open-label study.

The primary completion date is the last date that subject data was collected for the primary outcome measure.

The study completion date (End of Study) is defined as the last date that subject data was collected, which includes the safety follow-up telephone call visit. Procedures for when a subject is lost to follow-up are provided in [Section 4.6](#).

### **3.1.1 Open-label Treatment Period (52 Weeks)**

Subjects will be stratified by age group (5- through 12-year-olds or 13- through 17-year-olds). Subjects will remain in the age group they were stratified into during the antecedent double-blind study, throughout the OLE study.

All subjects will receive QD doses of pimavanserin over 52 weeks of treatment. Subjects will start at the “low dose” for their age group (10 mg for 5- through 12-year-olds; 20 mg for 13- through 17-year-olds) for the first two weeks. At the Week 2 visit, the daily dose may be adjusted to the “high dose” for their age group (20 mg for 5- through 12-year-olds; 34 mg for 13- through 17-year-olds), based on the Investigator’s assessment of clinical response. After the Week 2 visit and up to and including the Week 20 visit, dose adjustments, either increases or decreases, may be made at any clinic visit (scheduled or unscheduled), based on the Investigator’s assessment of clinical response and tolerability. No further dose adjustments are allowed after the Week 20 visit.

During the treatment period, clinic visits will be conducted at Baseline and Weeks 2, 6, 12, 20, 28, 36, 44, and 52, or upon early termination (ET) from the study.

Study drug will be dispensed to the subject to take home at the Baseline visit and at each subsequent clinic visit. The subject and their parent/legally acceptable representative (LAR) will be provided instructions for the subject’s first dose of study drug the day after the Baseline visit. It is recommended that the subject take the study drug at approximately the same time each day as a single, oral dose.

All concomitant medications should remain at a stable dose throughout the study, if possible, except as described in [Appendix A](#) to minimize confounding interpretation of any correlating pimavanserin dose changes, including treatment discontinuations.

### **3.1.2 Safety Follow-up Period (30 Days)**

A follow-up safety assessment will be conducted by telephone call at least 30 days after the last dose of study drug. The safety follow-up assessment will not be done if the subject (and/or parent/LAR) withdraws consent to participate in all parts of the study.

## **4 SUBJECT ELIGIBILITY AND WITHDRAWAL CRITERIA**

To be eligible for this study, subjects must meet all of the inclusion criteria and none of the exclusion criteria to enter this open-label extension study.

#### **4.1 Inclusion Criteria**

A subject must meet all of the following inclusion criteria to be eligible for participation in the study:

##### ***Study Population***

1. Has completed the treatment period of the antecedent double-blind study
2. Informed consent prior to the conduct of any study procedures is required as follows:
  - a. The subject should provide written or oral assent if deemed able by the Investigator.
  - b. The subject's parent/LAR must provide written consent. The subject's parent/LAR must be considered reliable by the Investigator, able to complete assessments regarding the subject's development and behavior throughout the study, and able to help ensure compliance with study treatment, study visits, and protocol procedures.
  - c. If a person other than the parent/LAR has been designated as a caregiver for the purpose of providing input for caregiver-reported scales, that person must also provide written consent. Such a designee should be a family member, adult and responsible, living with or in very frequent contact with the subject participating in the study, who is committed to providing responses for the caregiver-reported scales for the duration of the study.

The process of obtaining informed consent will be conducted in accordance with institutional review board (IRB) or ethics committee (EC) policy and applicable local law

3. In the Investigator's opinion, the subject, to the best of his/her ability, the parent/LAR, and the designated caregiver (if applicable, and in accordance with IRB or EC policy and applicable local law) are able to understand the nature of the study, follow protocol requirements and be willing to comply with study drug administration requirements

##### ***Psychiatric Diagnosis***

4. Continues to be both clinically stable and not at imminent risk of suicide or injury to self, others, or property, in the opinion of the Investigator
5. Continues to be medically stable at enrollment, in the opinion of the Investigator

### ***Contraceptives***

6. Female subjects who participate in this study must either be unable to become pregnant (e.g., premenarchal, surgically sterile, etc.) -OR- must agree to use two clinically acceptable methods of contraception (e.g., oral, intrauterine device [IUD], diaphragm plus spermicide, injectable, transdermal or implantable contraception) during the treatment period, and for at least 45 days after last dose.

All female subjects of childbearing potential must have a negative urine human chorionic gonadotropin (hCG) pregnancy test at Baseline and all clinic visits. Females of childbearing potential are defined as females who have begun menstruating.

## **4.2 Exclusion Criteria**

A subject must meet none of the following exclusion criteria to be eligible for the study:

### ***Study Population***

1. Subject or parent/LAR is judged by the Investigator to be inappropriate for the study (e.g., significantly noncompliant in the antecedent double-blind study)

### ***CNS, Psychiatric, and Illicit Drug Use Criteria***

2. Requires treatment with a medication prohibited by the protocol, including concomitant psychotropic drugs targeting irritability, including those used off-label (clonidine, guanfacine, and propranolol; lithium, valproate), medications that prolong the QT interval; and strong cytochrome P450 (CYP) 3A4 enzyme (CYP3A4) inhibitors and inducers (see [Appendix A](#) and [Appendix B](#))
3. Is at a significant risk of suicide, or is a danger to self or others, in the opinion of the Investigator based upon all available sources of information including C-SSRS (positive answer to suicidal ideation questions 4 or 5 [or positive answer to suicidal behavior questions at Baseline])
4. Is at risk of significant violent behavior to the extent that participation would pose an undue risk to other patients, caregivers, or others in the opinion of the Investigator
5. Has a positive urine drug test at Baseline. For study eligibility, the urine toxicology (drug) screen (UDS) must be negative for any substance for which the subject does not have a valid prescription.

### ***Medical Criteria***

6. Has developed a serious and/or unstable psychiatric, neurologic, cardiovascular (e.g., long QT syndrome, torsade de pointes, unstable cardiac syndrome or syncope, congestive heart failure, ongoing uncorrected hypokalemia or hypomagnesemia, non-sustained or sustained ventricular tachycardia), respiratory, gastrointestinal, renal, hepatic, hematologic, or other medical disorder, including cancer or malignancies that, in the judgment of the Investigator, would jeopardize the safe participation of the subject in the study, or has major surgery planned during the study
7. Has experienced any change in medical or treatment status that may increase the risk associated with taking pimavanserin, would interfere with safety assessments, or would confound the interpretation of study results, based on the Investigator's judgment
8. For age <13 years, a resting position (sitting or supine) systolic (SBP) and/or diastolic blood pressure (DBP) level  $\geq$ 90th percentile for gender-specific age and height charts from the National Heart and Lung Institute (NHLI), at Baseline. For age  $\geq$ 13 years a resting position (sitting or supine) SBP  $\geq$ 120 mmHg and/or a DBP  $\geq$ 80 mmHg, at Baseline.
9. Has a clinically significant abnormal ECG at Baseline or any of the following cardiac conduction abnormalities:
  - a. Corrected QT interval using Fridericia's correction method (QTcF)  $\geq$ 450 ms
  - b. PR interval on ECG  $>$ 220 ms
  - c. Evidence of second- or third-degree atrioventricular block
  - d. Evidence of complete left bundle branch block
  - e. Intraventricular conduction delay with QRS interval on ECG (QRS)  $>$ 110 ms
  - f. QRS or T wave morphology that could, in the Investigator's opinion, render QT interval assessment unreliable
  - g. Sick sinus syndrome
  - h. Non-sinus rhythm
  - i. Resting heart rate  $<$ 50 beats per minute

One repeat set of triplicate ECGs is allowed at Baseline.

10. Weight  $<$ 15 kg
11. *In Italy only:* Has a sensitivity to any compound present in pimavanserin or any metabolites or compounds listed in the Investigator's brochure as being present in this medication

#### **4.3 Screen Failures**

The Investigator will maintain a screening log to record details of all participants screened and to confirm eligibility or record reasons for screening failure, as applicable.

#### **4.4 Subject Withdrawal of Consent**

In accordance with the Declaration of Helsinki and other applicable regulations, a subject has the right to withdraw from the study at any time, and for any reason, without prejudice to his or her future medical care.

If the subject (and/or parent/LAR) decides to withdraw consent from all components in the study, this must be documented and no additional assessments will be performed. The Sponsor may retain and continue to use any data collected before such a withdrawal of consent. The subject may request destruction of any samples taken and not tested, prior to their withdrawal of consent, and the Investigator must document this in the site study records.

If the subject (and/or parent/LAR) wants to discontinue treatment and agrees to the evaluations specified at the EOT/ET visit and/or at safety follow up (whichever is applicable), as outlined in [Table S-1](#), the agreed assessments should be conducted. The subject's reason for wanting to discontinue treatment and the agreement to continue with the applicable assessments for study termination must be documented.

Every reasonable effort should be made to keep the same parent/LAR or designee who completed the observer's study scales in study ACP-103-069 to complete them throughout study ACP-103-070 in order to maintain the validity of the scoring.

#### **4.5 Subject Discontinuation**

Subjects may be discontinued from the study treatment for a number of reasons, including, but not limited to, those listed below:

- Adverse event
- Death
- Lack of efficacy
- Lost to follow-up ([Section 4.6](#))
- Non-compliance with study drug
- Physician decision
- Pregnancy
- Protocol deviation

- Study terminated by sponsor
- Use of prohibited medication
- Withdrawal of consent by subject (or by parent/LAR)
- Other

#### **4.5.1 Handling of Subject Discontinuation During the Treatment Period**

Unless the subject (or parent/LAR) has withdrawn consent from all components of the study, every reasonable effort should be made to complete Visit 6/ET and the safety follow-up visit (as outlined in [Table S-1](#)) if a subject discontinues prematurely during the treatment period of the study. All information will be reported on the applicable pages of the electronic case report form (eCRF).

If a subject is discontinued from the study treatment because of an AE, every reasonable attempt should be made to follow and appropriately treat (or refer for treatment) the subject until the AE resolves or until the Investigator deems the AE to be chronic or stable. For subjects who continue to be followed for safety, serious adverse events (SAEs) should continue to be reported as described in [Section 7.4.2](#). All SAEs will continue to be followed and appropriately treated until such events have resolved or the Investigator deems them to be chronic or stable.

#### **4.6 Subject Lost to Follow-up**

A subject will be considered lost to follow-up if they fail to attend a scheduled visit (including the safety follow-up visit) and the study subject or parent/LAR is unable to be contacted by the study site **after repeated attempts**.

Every reasonable effort should be made to contact the subject and parent/LAR and will include a minimum of three documented phone calls and, if necessary, a certified letter to the subject's last known mailing address or local equivalent methods. All contact attempts are to be documented in the source documents.

#### **4.7 Study Discontinuation**

The Sponsor reserves the right to discontinue the study at any time for any reason. Such reasons may be any of, but not limited to, the following:

- Occurrence of AEs unknown to date in respect of their nature, severity, and duration or the unexpected incidence of known AEs
- Medical, ethical, or business reasons affecting the continued performance of the study

Regulatory authorities also have the right to terminate the conduct of the study in their region for any reason.

## **4.8 Prior and Concomitant Therapy**

All medications used from study baseline until completion of the safety follow-up visit are to be recorded.

### **4.8.1 Prior Medication**

Prior medication is defined as any medication with a stop date prior to the date of the first dose of study drug.

### **4.8.2 Concomitant Medication**

Concomitant medication is defined as any medication that is ongoing at the first dose of study drug or with a start date between the dates of the first dose and last dose of study drug, inclusive.

In order to ensure that appropriate concomitant therapy is administered, it is essential that subjects be instructed not to take any medication without prior consultation with the Investigator (unless the subject is receiving treatment for a medical emergency). Non-pharmacological treatment should remain the same throughout the study duration.

The Investigator may prescribe appropriate medication to treat AEs (see [Appendix A](#) and [Appendix B](#)).

#### **4.8.2.1 Permitted, Restricted, and Prohibited Medications**

Prohibitions and restrictions for concomitant medications should be followed between the Baseline visit and Visit 6/EOT/ET as specified in [Appendix A](#) and [Appendix B](#). These appendices do not constitute an exhaustive list and any questions regarding prohibited and restricted medications should be discussed with the Medical Monitor or designee. The Investigator may prescribe appropriate medication to treat AEs.

Medications that can prolong QT interval are prohibited (or restricted) as specified in [Appendix A](#).

Permitted concomitant medications should remain at a stable dose throughout the treatment period.

If a subject is on a medication restricted by the protocol, the medication should be adjusted if it is determined by the Investigator to be clinically appropriate (e.g., if the subject's symptoms are not well-controlled or if the subject cannot tolerate the current medication) in consultation with the treating physician.

Subjects who require current treatment with a prohibited medication will be withdrawn from the study.

Subjects who have taken a prohibited medication during the study will be withdrawn from the study unless:

- the prohibited medication has been discontinued, AND
- withdrawal from the study presents an unacceptable medical risk to the subject

The justification to allow the subject who has taken a prohibited medication to continue in the trial will be made by the Sponsor/Medical Monitor, with medical input from the Investigator, and will be documented. If a subject is allowed to remain in the trial, this will be reported as a major protocol deviation and not a waiver.

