**“WARNING: INCREASED MORTALITY IN ELDERLY PATIENTS WITH DEMENTIA-RELATED PSYCHOSIS”**

The increased mortality warning in elderly patients with dementia-related psychosis is based on information regarding antipsychotic drugs in general, rather than specific pimavanserin data.

The Warnings and Precautions section of the Prescribing Information for pimavanserin also includes information about QT interval on ECG (QT) interval prolongation. Pimavanserin prolongs the QT interval. The use of pimavanserin should be avoided in patients with known QT prolongation or in combination with other drugs known to prolong QT interval including Class 1A antiarrhythmics (e.g., quinidine, procainamide) or Class 3 antiarrhythmics (e.g., amiodarone, sotalol), certain antipsychotic medications (e.g., ziprasidone, chlorpromazine, thioridazine), and certain antibiotics (e.g., gatifloxacin, moxifloxacin). Pimavanserin should also be avoided in patients with a history of cardiac arrhythmias, as well as other circumstances that may increase the risk of the occurrence of torsade de pointes and/or sudden death, including

symptomatic bradycardia, hypokalemia or hypomagnesemia, and the presence of congenital prolongation of the QT interval.

NUPLAZID is contraindicated in patients with a history of a hypersensitivity reaction to pimavanserin or any of its components. Rash, urticaria, reactions consistent with angioedema (e.g., tongue swelling, circumoral edema, throat tightness, and dyspnea) have been reported. In addition, adverse reactions of somnolence, falls, agitation, and aggression have been reported during postapproval use of NUPLAZID.

Pimavanserin has not yet been studied as monotherapy in children and adolescents therefore no data are available on specific risks in this population. In adolescents treated with pimavanserin in combination with other psychotropics, pimavanserin dose-related QTc prolongation, and a trend for higher exposure with decreasing age and decreasing body weight, have been observed.

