**Table 6–1 Safety Laboratory Evaluations**

Visit	Tests
Visit 1 (Baseline)	CHEM, CBC, UA, urine toxicology screen and dipstick, urine pregnancy test
Visit 2 (Week 2)	Urine pregnancy test
Visit 3 (Week 6)	Urine pregnancy test
Visit 4 (Week 12)	CHEM, CBC, UA, urine pregnancy test
Visit 5 (Week 20)	Urine pregnancy test
Visit 6 (Week 28)	CHEM, CBC, UA, urine pregnancy test
Visit 7 (Week 36)	Urine pregnancy test
Visit 8 (Week 44)	CHEM, CBC, UA, urine pregnancy test
Visit 9 (ET/EOT)	CHEM, CBC, UA, urine toxicology screen, urine pregnancy test

Abbreviations: CBC=complete blood count; CHEM=clinical chemistry serum tests; EOT=end of treatment; ET=early termination; UA=urinalysis

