	UNRESTRICTED 
 
• peripherally acting anticholinergics
 
• topical diphenhydramine
 
	Peripherally acting anticholinergic medications and topical diphenhydramine are allowed without restriction
Anticonvulsant and mood stabilizers	PROHIBITED 
 
• carbamazepine
 
• lamotrigine
 
• lithium
 
• oxcarbazepine
 
• phenytoin
 
• valproate
 
	Prohibited throughout the treatment period
Antidepressants	PROHIBITED 
 
• amitriptyline
 
• citalopram
 
• clomipramine
 
• desipramine
 
• desvenlafaxine
 
• doxepin
 
• duloxetine
 
• escitalopram
 
• esketamine
 
• fluvoxamine
 
• fluoxetine
 
• imipramine
 
• ketamine
 
• mianserin
 
• mirtazapine
 
	Prohibited throughout the treatment period

Medication Class	Medication a	Prohibition/restrictions
	
 
nefazadone
 
nortriptyline
 
sertraline
 
trazodone
 
trimipramine
 
venlafaxine
 
	
Antimanic agents	PROHIBITED 
 
lithium
 
valproate
 
	Prohibited throughout the treatment period
Antimicrobials, antifungals, and antimalarials	PROHIBITED 
 
clarithromycin
 
erythromycin
 
levofloxacin
 
moxifloxacin
 
pentamidine
 
roxithromycin
 
 RESTRICTED 
 
artenimol/piperaquine
 
azithromycin
 
bedaquiline
 
ciprofloxacin
 
fluconazole
 
gemifloxacin
 
norfloxacin
 
ofloxacin
 
telavancin
 
telithromycin
 
	Prohibited throughout the treatment period
Antipsychotics other than pimavanserin	PROHIBITED All in class	Prohibited throughout the treatment period

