## Appendix B Prohibited and Restricted Concomitant Medications: Inhibitors and Inducers of Cytochrome P450 Enzyme 3A4

The information presented here is intended to provide guidance and does not constitute an exhaustive list of strong CYP 3A4 enzyme (CYP3A4) inhibitors and inducers. Any questions should be discussed with the Medical Monitor or appropriate designee.

Subjects who require current treatment with a prohibited medication will be withdrawn from the study.

Subjects who have previously taken a prohibited medication during the study will be withdrawn from the study unless:

- the prohibited medication has been discontinued AND
- withdrawal from the study presents an unacceptable medical risk to the subject

The justification to allow the subject to continue in the study will be made by the Sponsor/Medical Monitor with medical input from the Investigator, and will be documented. If allowed to remain in the study, this will be reported as a major protocol deviation and not a waiver.

The metabolism of pimavanserin is affected by strong CYP3A4 inhibitors, resulting in an increase in Cmax and AUC of approximately 3-fold.

Strong inhibitors of CYP3A4 are to be stopped at least 2 weeks or 5 half-lives prior to investigational product administration, whichever is longer. Strong inducers of CYP3A4 are to be stopped 30 days or 5 half-lives prior to investigational product administration, whichever is longer. Moderate inhibitors and inducers of CYP3A4 are allowed but should be used with caution.

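### Protocol 4.8.2.1 and 4.5.1 name Visit 6 (Week 28) where Visit 9 (Week 52) is meant, and the rescue limit and restricted-drug dose rule do not line up with Appendix A

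*Protocol*

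**What the plan says.** **Visit number.** Protocol 4.8.2.1 states that the prohibitions and restrictions "should be followed between the Baseline visit and Visit 6/EOT/ET". Protocol 4.5.1 asks that, for a subject who stops early, "every reasonable effort should be made to complete Visit 6/ET and the safety follow-up visit", and points to Table S-1 for the content. Table 6-1 lists "Visit 6 (Week 28") and places ET/EOT at Visit 9. Table S-1 agrees, with Visit 9 at Week 52.

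**What the appendices add.** Appendix A marks most of its prohibited classes "Prohibited throughout the treatment period". Appendix B gives wash-out times ("Strong inhibitors of CYP3A4 are to be stopped at least 2 weeks or 5 half-lives prior to investigational product administration, whichever is longer", with a 30-day counterpart for strong inducers). It also has a withdrawal rule for subjects who need a prohibited drug or have taken one during the study. It gives no on-treatment period of its own.

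**Rescue.** Protocol 4.8.3 sets a ceiling of 7 consecutive days, subject to Appendices A and B. The anxiolytics row of Appendix A repeats the 7 days for lorazepam, then provides for longer use after reassessment and discussion with the Medical Monitor.

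**Restricted drugs.** Under 4.8.2.1, for a subject on a restricted drug, "the medication should be adjusted if it is determined by the Investigator to be clinically appropriate"; its examples are poorly controlled symptoms and intolerance. Appendix A admits atomoxetine, and stimulants and wake-promoting agents, only if the dose was stable in the antecedent study and is expected not to change. Section 3.1.1 asks for stable concomitant doses where possible, except as Appendix A describes.

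**Analysis.** SAP 13.2 computes responder rates on observed cases. SAP 11 tabulates concomitant medication by class and preferred term. No planned table relates that use to response.

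**The concern.** These are instructions that sites apply for a year, and each can be read in two ways.

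The visit number has a safety side. Appendix B says strong CYP3A4 inhibitors raise pimavanserin Cmax "and AUC of approximately 3-fold", and Protocol 1.5.1 says "Pimavanserin prolongs the QT interval". Several strong inhibitors and inducers, such as itraconazole, ketoconazole and rifampin, are named only in Appendix B, so 4.8.2.1 is the text that dates the rule for them. In 4.5.1, a literal Visit 6 would omit the urine toxicology screen that Table 6-1 assigns to ET/EOT.

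On rescue, a site that uses lorazepam on day 8 after speaking to the Medical Monitor complies with Appendix A and breaches 4.8.3, so deviations could be classified inconsistently. On restricted drugs, two sites could reach opposite answers on whether a stimulant dose may be raised.

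The analytic question is smaller. The only secondary endpoint, the Week 52 composite of ABC-I and CGI-I, is scored whatever other drug was added or increased, although 3.1.1 itself gives confounding as the reason for wanting stable doses.

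**Working it through.** The plan gives no figure on this point. Its one precision figure, the Rule of Three bound in Protocol 9.3, reproduces (3/193 = 1.55%, stated as 1.6%) and is unaffected. The check is mainly a comparison of texts.

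1. **Which visit.** Table S-1 pairs Weeks 0, 2, 6, 12, 20, 28, 36, 44 and 52 with Visits 1 to 9. Visit 6 is therefore Week 28 and Visit 9 is Week 52. Table 6-1 gives the same pairing and labels Visit 9 ET/EOT. The number in 4.8.2.1 and 4.5.1 is wrong in both places.

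2. **Span of a literal reading.** 52 − 28 = 24 weeks; 24/52 = 46.2% of the treatment period. From SAP Table 2, the Week 28 target is Study Day 197 and the Week 52 window opens on Study Day 337: 337 − 197 = 140 days.

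3. **How much of that span other text covers.**
   - 4.8.2.1 names EOT/ET next to the visit number.
   - 4.5.1 defers to Table S-1 for what is done.
   - Appendix A's prohibitions run through treatment. They include some strong CYP3A4 agents by name (clarithromycin, carbamazepine, phenytoin).
   - Appendix B withdraws subjects who require a prohibited drug or have taken one during the study, with a narrow exception.

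   What remains is a wrong label and, for drugs named only in Appendix B, no explicit dated on-treatment rule outside 4.8.2.1.

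4. **Rescue.** 4.8.3: 7 consecutive days, no exception in its own words. Appendix A: 7 days for lorazepam, with a route beyond. The two differ from day 8 onward, for lorazepam or the substitute benzodiazepine that Appendix A allows.

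5. **Restricted drugs.** 4.8.2.1 directs adjustment on clinical grounds. Appendix A conditions use on an expected constant dose. The texts can be reconciled if the Appendix A condition applies only at entry, but neither says so.

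6. **Optional responder row.** Let *m* be the number assessed at Week 52 and *k* the number of composite responders on rescue or on newly started or increased behavioural medication. Planned rate minus supplementary rate = *k*/*m*, which is zero or positive.
   - One such responder, all 193 assessed: 1/193 = 0.52 percentage points.
   - One such responder, 50% retention (assumed): 193 × 0.5 ≈ 97; 1/97 = 1.03 points.
   - With assumed response of 40% or 60% and an assumed 5% to 20% of responders affected, the gap runs from 0.40 × 0.05 = 2 points to 0.60 × 0.20 = 12 points. This range only multiplies assumptions and is not an estimate; the documents supply neither input.

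**The case against.** The strongest reply is that no competent site would stop applying the medication rules at Week 28. Both sentences name EOT or ET, 4.5.1 points to Table S-1, and Appendix B's withdrawal rule covers the whole study. **That stands**, and it is why the point is minor. A reader might infer that children could take strong CYP3A4 inhibitors without restriction for the last 24 weeks, with the attendant QT risk. The documents do not support that.

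On rescue, 4.8.3 already refers to Appendix A, so the route beyond 7 days could be taken as incorporated. That narrows the conflict but does not remove it, since a stated maximum and a route past it still differ.

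On restricted drugs, a reader might infer that Appendix A forbids any stimulant or atomoxetine increase. The documents do not settle this. Section 4.8.2.1 gives poorly controlled symptoms as a ground for adjustment, which points if anything toward an increase or a switch. It also sends questions to the Medical Monitor. A ban would be a policy choice affecting children's care, not a clarification.

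On the responder rate, scoring observed response regardless of other medication is a legitimate choice in a descriptive study with no testing. Existing safeguards are real:
- Exclusion 2 removes drugs that target irritability.
- Benzodiazepines for anxiety may not be taken within 12 hours before an assessment visit.
- Prohibited-drug users who are allowed to stay are reported as major deviations, which SAP 7 summarises.

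A reader might infer that the planned rate is inflated. No passage says that stimulants or benzodiazepines improve ABC-I or CGI-I, so that inference is unsupported. This objection also stands.

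**Conclusion.** The visit number is wrong in two operative sections and should be Visit 9 in both. The effect is small because the intended end of the rules can be recovered from the surrounding text; the 24 weeks (46%) measure only the literal reading. The rescue texts conflict narrowly, from day 8 of lorazepam or its substitute. The dose-change texts are in tension for stimulants, wake-promoting agents and atomoxetine, and the sponsor needs to say which one governs. Overall severity is minor. Confidence is high on the visit number and the rescue mismatch, and lower on the dose rule, where a reconciling reading exists.

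The supplementary Week 52 row is a suggestion, not the correction of an error. With no control arm, neither rate would establish a drug effect. The row would leave the observed-case denominator, and hence dropout, untouched.

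**What to change.** - **Protocol 4.8.2.1 and 4.5.1:** change Visit 6 to Visit 9 in each. Two numerals.
- **Protocol 4.8.3:** add one sentence carrying over the Appendix A exception: lorazepam, or the substitute benzodiazepine, may continue past 7 days only after reassessment and discussion with the Medical Monitor.
- **Protocol 4.8.2.1 or Appendix A:** add one sentence saying whether the adjustment clause or the constant-dose condition governs for stimulants, wake-promoting agents and atomoxetine once a subject is enrolled. The choice is the sponsor's.
- **SAP 13.2, optional:** keep the planned Week 52 composite rate and add one descriptive row on the same denominator that counts as non-responders those responders on rescue or on newly started or increased behavioural medication. Define the drugs and look-back windows in advance and label them as conventions. State how incomplete dates are handled, because SAP 5.4.2 only settles whether a drug counts as concomitant.

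Cost: the protocol edits can go into one amendment or notification under Protocol 10.7. Sample size and the planned tables do not change. The optional row needs dose-change and indication data. Protocol 4.8 has all medications recorded, but the documents do not confirm those fields, so the row may be only partly derivable.
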